11.6.5.2 Pregnancy

Subjects will be counseled to inform the investigator of any pregnancy that occurs during the study.

If a subject or the female partner of a male subject becomes pregnant during the study, the investigator will notify the medical monitor and Vertex GPS within 24 hours of the site's knowledge of the subject's (or partner's) pregnancy using the Pregnancy Information Collection Form.

If confirmed to have been treated with active drug, the subject or partner will be followed until the end of the pregnancy and the infant will be followed for 1 year after the birth, provided informed consent is obtained. A separate ICF will be provided to explain these follow-up activities. Pregnancy itself does not constitute an AE.

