10.10.2 Unblinding

At the initiation of the study, the study site will be instructed on the method for breaking the blind. The unblinding method will be either a manual or electronic process.

Unblinding of the individual subject's treatment by the investigator will be limited to medical emergencies or urgent clinical situations in which knowledge of the subject's study treatment is necessary for clinical management. In such cases, investigators will use their best judgment as to whether to unblind without first attempting to contact the medical monitor to discuss and agree to the need for unblinding. If investigators deem it not necessary to unblind immediately, they will first attempt to contact the medical monitor to discuss and agree to the need for unblinding. If investigators have tried, but are unable to reach the medical monitor, they will use their best judgment, based on the nature and urgency of the clinical situation, and may proceed with unblinding without having successfully reached and discussed the situation with the medical monitor.

Contact information for the medical monitor (or appropriate backup) will be provided in a separate document.

In addition, the Vertex Medical Information Call Center [REDACTED] will answer calls 24 hours a day, 7 days a week, 365 days of the year, and will triage these calls to the study medical monitor or appropriate backup.

If a subject's treatment assignment has been unblinded for a medical emergency or urgent clinical situation, the medical monitor will be notified within 24 hours of the unblinding event. The reason and the date of the unblinding will be documented clearly in the subject's study file. Information about the treatment assignment obtained from the unblinding will be maintained in a secure location with controlled access and will not be shared with the sponsor (Vertex), contract research organization (CRO), or any site personnel (other than the physician treating the subject). In addition, the investigator will consider whether the clinical event that prompted unblinding will be considered an SAE, according to the regulatory

definitions or criteria for SAEs, and if so, submit an SAE report to Vertex GPS or designee, per Section 13.1.2.

Vertex GPS or designee will also unblind any SAE reports in compliance with regulatory reporting requirements. In addition, Vertex may, for matters relating to safety concerns, unblind individual subjects at any time.

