7.4.2 Unblinding

At the initiation of the study, the study site will be instructed on the method for breaking the blind. The unblinding method will be either a manual or electronic process.

Unblinding of the individual subject's treatment by the investigator will be limited to medical emergencies or urgent clinical situations in which knowledge of the subject's study treatment

is necessary for clinical management. In such cases, investigators will use their best judgment as to whether to unblind without first attempting to contact the medical monitor to discuss and agree to the need for unblinding. If investigators deem it not necessary to unblind immediately, they will first attempt to contact the medical monitor to discuss and agree to the need for unblinding. If investigators have tried, but are unable to reach the medical monitor, they will use their best judgment, based on the nature and urgency of the clinical situation, and may proceed with unblinding without having successfully reached and discussed the situation with the medical monitor.

Contact information for the medical monitor (or appropriate backup) will be provided in a separate document.

In addition, the Vertex Medical Information Call Center [REDACTED] will answer calls 24 hours a day, 7 days a week, 365 days of the year, and will triage these calls to the study medical monitor or appropriate backup.

If a subject's treatment assignment has been unblinded for a medical emergency or urgent clinical situation, the medical monitor will be notified within 24 hours of the unblinding event. The reason and the date of the unblinding will be documented clearly in the subject's study file. Information about the treatment assignment obtained from the unblinding will be maintained in a secure location with controlled access and will not be shared with the sponsor (Vertex), contract research organization (CRO), or any site personnel (other than the physician treating the subject). In addition, the investigator will consider whether the clinical event that prompted unblinding will be considered an SAE, according to the regulatory definitions or criteria for SAEs, and if so, submit an SAE report to Vertex GPS or designee, per Section 13.1.2 of the protocol.

Vertex GPS or designee will also unblind any SAE reports in compliance with regulatory reporting requirements. In addition, Vertex may, for matters relating to safety concerns, unblind individual subjects at any time.

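### Pregnancy follow-up conditional on confirmed active drug opens a route to unblinding and leaves placebo pregnancies without planned outcome follow-up

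*Protocol*

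**What the plan says.** **Reporting covers both arms.** Protocol 11.6.5.2 begins: "If a subject or the female partner of a male subject becomes pregnant during the study, the investigator will notify the medical monitor". The sponsor's safety group is also told, within 24 hours, on the Pregnancy Information Collection Form. This step does not depend on treatment.

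**Follow-up covers one arm.** The section continues: "If confirmed to have been treated with active drug, the subject or partner will be followed until the end of the pregnancy". In the same sentence, "the infant will be followed for 1 year after the birth, provided informed consent is obtained". It then adds: "A separate ICF will be provided to explain these follow-up activities". Nothing parallel is planned for placebo. The section does not say who confirms treatment, when, or who is told. It also states that pregnancy is not in itself an adverse event.

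**Blinding rules.** Protocol 10.10.2 says: "Unblinding of the individual subject's treatment by the investigator will be limited to medical emergencies or urgent clinical situations". SAP 7.4.2 repeats the limit. Information from such an unblinding "will not be shared with the sponsor (Vertex), contract research organization (CRO), or any site personnel (other than the physician treating the subject"). The same section lets the sponsor unblind individual subjects at any time over safety concerns. Protocol 10.10.1 and SAP 7.4.1 exempt the sponsor's safety and regulatory staff from the blind only as regulatory reporting requires. None of these sections names pregnancy.

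**Other safety capture.** Protocol 13.1.2.1 counts a congenital anomaly or birth defect as an SAE. Protocol 13.1.2.2 has SAEs reported in both arms, whatever their cause, through the follow-up visits. After the study has concluded, only those considered related to study drug are reported.

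**The concern.** A rule that starts a visible activity in only one arm discloses the arm when it is applied. Here the activity is a consent discussion followed by months of contact with the subject or partner, which cannot be hidden from them or from the site staff who carry it out.

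Two things are at stake. The first is the blind for the affected subjects. UEMS comes from the ISNCSCI examination, scheduled with SCIM III at 6 weeks and 3, 6 and 12 months; CUE-T and GRASSP are scheduled at 6 months. These measures depend partly on the subject's effort and on an examiner's scoring. The second is the shape of the safety data. Both arms undergo the same surgery and receive fibrin sealant, yet pregnancy and infant outcomes are planned to be complete for VX-210 only.

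**Working it through.** The documents give no pregnancy rate and no figure on this point, so there is no stated number to reproduce. The check sets the sections side by side and then bounds the size.

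**1. Does applying the rule disclose the arm?**
- Follow-up and its consent form depend on active drug being confirmed (Protocol 11.6.5.2).
- Following a pregnancy to its end normally means starting while it is ongoing.
- If that happens during blinded participation, an offer after a reported pregnancy implies VX-210 and no offer implies placebo. Both arms are exposed.
- Sponsor-side confirmation does not prevent this. Even if only the sponsor's safety staff look up the allocation, approaching the subject or partner passes the result on.

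**2. Is there a permitted route to the confirmation?**
- Investigator unblinding is confined to emergencies and clinically urgent cases. An uncomplicated pregnancy is not obviously either.
- The exemption for sponsor safety staff is tied to regulatory reporting.
- The sponsor's power to unblind over safety concerns is the remaining route. It permits the lookup but contains nothing that keeps the site or subject blinded afterwards.

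**3. What is collected for placebo pregnancies?** The initial report, and SAEs through the follow-up visits. Participation lasts about 12 months (Protocol 8.1). Assuming a gestation of about 9 months:
- a conception after about month 12 − 9 = 3 delivers after the last visit;
- a conception immediately after treatment leaves at most about 12 − 9 = 3 months of infant observation, against 1 year in the VX-210 arm.

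The gap is therefore outcome to term for most conceptions, and the 1-year infant data for all of them.

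**4. How many subjects?** Assume k = 0 to 4 pregnancies among about 100 subjects and their partners. At most k/100 = 0% to 4% of allocations could be inferred. Under 1:1 randomization, the chance that at least one pregnancy is on active drug is 1 − 0.5^k: 50% for k = 1, 75% for k = 2 and 88% for k = 3.

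**5. Effect on the primary endpoint.** Inputs: 45 followed subjects per arm (50 less 10% withdrawal), SD 6 and a target difference of 4 points, all from Protocol 12.1. Assume 2 subjects in one arm are unblinded before the 6-month examination, each with UEMS biased by b points in the same direction.
- Shift in the arm mean = 2b/45.
- b = 2: 4/45 = 0.09 points. b = 4: 8/45 = 0.18 points.
- SE of the difference = 6 × √(2/45) = 1.26 points.
- The shift is 0.09/1.26 = 7% to 0.18/1.26 = 14% of one SE, and 0.09/4 = 2% to 0.18/4 = 4.5% of the target difference.

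**The case against.** The case against has real substance.

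- **Timing and recipient are not stated.** A reader might infer that every reported pregnancy reveals the arm to the site mid-trial. The documents do not support that. Protocol 11.6.5.2 sets no time for the confirmation and names no one to receive it. Under Protocol 12.3.5.1 the primary analysis follows a lock after all treated subjects have passed 6 months, so a late pregnancy might be confirmed only after that. Disclosure follows when the rule is acted on during blinded follow-up, not in every case.
- **No direct contradiction with 10.10.2 is shown.** A reader might infer one. However, the emergency limit governs the investigator, the restriction on sharing concerns information from that kind of unblinding, and the sponsor may unblind over safety concerns. What stands is narrower: pregnancy is not a named ground, and the available route does not protect the blind once follow-up begins.
- **Placebo pregnancies are not lost altogether.** A reader might infer that none would be on record. They are reported on the collection form, and SAEs including birth defects are captured in both arms through the follow-up visits. What is missing is planned follow-up to term and to 1 year.
- **The size is small.** Contraception by two methods is required, with waivers (Protocol 11.6.5.1), and examinations are done by independent, trained assessors. With 0 to 4 pregnancies no comparison between arms would be precise, and the safety analysis sections plan no summary of pregnancy outcomes. Limiting long follow-up to exposed pregnancies is also a recognizable design choice.

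These arguments limit the size and certainty of the problem. They do not remove the one-sided rule or the inference that it permits.

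**Conclusion.** The point holds as a minor, inexpensive improvement. Protocol 11.6.5.2 ties follow-up to term and 1-year infant follow-up to confirmed active drug. Acting on it during blinded follow-up lets the site and the subject or partner infer the arm, through a route that the blinding sections do not address. It also plans pregnancy-outcome data for one arm only.

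The effect on UEMS is negligible: about 0.09 to 0.18 points against a target of 4, and only if 2 of 45 subjects were each biased by 2 to 4 points in the same direction. Those counts and biases are assumptions, as is the range of 0 to 4 pregnancies; the documents give no basis for any of them. A reader might infer that the primary result is threatened or that an informative safety comparison is forfeited. Neither follows at these numbers.

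**What to change.** In Protocol 11.6.5.2, delete the opening condition on confirmed active drug. Every reported pregnancy, in a subject or a partner, would then be offered the same consented data-collection follow-up and the same consent form regardless of arm, with no unblinding for this purpose. Allocation is added from the randomization list after database lock. This concerns data collection only.

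The cost is a protocol amendment and follow-up of the few placebo-arm pregnancies: 0 to 2 expected if 0 to 4 occur and split evenly.

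If the sponsor keeps the condition, 11.6.5.2 must be reconciled with Protocol 10.10.1 and 10.10.2 and SAP 7.4. The text should state who confirms treatment, when, who is told, and how the site, subject and efficacy assessor stay blinded once follow-up begins. Naming a sponsor-side confirmer would not be enough, because the follow-up itself discloses the arm.

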11.6.6 Immunogenicity Measures

11.6.6.1 Serum Sampling

Serum samples will be collected at visits indicated in [Table 3-1](#) and will also be collected at the time of any SAE occurring within 3 days after treatment.

The following will be recorded accurately in the source document: date and time of administration of the dose; date and time of each of the immunogenicity serum samples.

11.6.6.2 Processing and Handling of Immunogenicity Samples

Detailed procedures for the collection of serum samples and further procedures for processing and handling of samples for immunogenicity analysis will be provided in the Laboratory Manual and Sample Handling Guidelines. The shipment address and assay laboratory contact information will be provided to the investigational site before initiation of the study.

11.6.6.3 Bioanalysis

Samples will be analyzed using a validated analytical method in compliance with Vertex or designee standard operating procedures. A description of the assay and validation data will be provided in separate reports.

12 STATISTICAL AND ANALYTICAL PLANS

This section presents a summary of the planned analyses for this protocol. Statistical analysis details will be provided in the statistical analysis plan (SAP), and clinical pharmacologic analysis details will be provided in the clinical pharmacology analysis plan (CPAP), both of which will be finalized before the clinical data lock for the study and treatment unblinding.

12.1 Sample Size and Power

The primary efficacy endpoint is the change from baseline in UEMS at 6 months after treatment.

The null hypothesis to be tested is that the mean change from baseline in UEMS at 6 months after treatment is the same for 9-mg dose of VX-210 and placebo. This null hypothesis will be tested at 2-sided significance level $\alpha = 0.05$.

The sample size was calculated using a projected standard deviation (SD) of 6.0, based on the variability of improvement in UEMS scores of cervical subjects in the historical Sygen database. Anticipated withdrawal of 10% of subjects before the first follow-up assessment was also included in the sample size calculation.

If 9-mg dose group improves in UEMS by 4 points over placebo (a clinically meaningful increase), a total of approximately 100 subjects (approximately 50 per arm) will have

approximately 82.1% power to detect a statistically significant treatment effect for 9-mg dose group compared to placebo, considering the interim futility analysis.

Based on the review of data from Anderson et al.,³⁸ the SD was projected to be 3.8 for SCIM III Self-Care subscore. Table 12-1 presents the estimated power for detecting different treatment differences between an active treatment group and the placebo group in SCIM III Self-Care subscore, assuming 45 randomized subjects with follow-up assessment in each treatment group without considering the possible power loss from the interim futility analysis.

Table 12-1 Power Estimates Under a Variety of Treatment Differences, Given 45 Randomized Subjects With Follow-up Assessments in Each Treatment Group

Mean Difference in SCIM III Self-Care Subscore	Power (%)
1	23
2	69
3	95

Power estimates are based on 2-sided t-test with $\alpha = 0.05$.

12.2 Analysis Sets

Assignment of subjects to analysis sets will be performed before the clinical data lock for the study and treatment unblinding.

The All Subjects Set is defined as all subjects who have been randomized or have received study drug. This analysis set will be used in subject listings and disposition summary table, unless otherwise specified.

The Full Analysis Set (FAS) is defined as all randomized subjects who have received study drug. The FAS is to be used in efficacy analyses in which subjects will be analyzed according to their randomized treatment group and not to the treatment they actually received.

The Safety Set is defined as all subjects who have received study drug. The Safety Set is to be used for all safety analyses in which subjects will be analyzed according to the treatment they received and not according to their randomized treatment group.

12.3 Statistical Analysis

The primary objectives of this study are to evaluate the efficacy and safety of VX-210 treatment in subjects with acute traumatic cervical SCI. The primary analyses will be based on the 6 month data. [REDACTED]

This section presents a summary of the planned statistical analyses of efficacy and safety for this study. The Vertex Biometrics department or a designated CRO will analyze the data derived from this study. Statistical Analysis System Version 9.2 or higher will be used to generate all statistical outputs (tables, figures, listings, and data sets).

Statistical analysis and presentation details will be provided in the SAP for the study.

12.3.1 General Considerations

All individual subject data for all individual subjects randomized or received study drug will be presented in data listings.

Continuous variables will be summarized using the following descriptive summary statistics: the number of subjects (n), mean, SD, standard error (SE), median, minimum value (min), and maximum value (max). The precision of the measurement for each continuous variable will be used to determine the number of decimal places to present in tables, figures, and derived listings. Unless otherwise specified, min and max values will be reported with the same precision as the units of measure; the mean, median, SD, and SE will be reported to 1 greater decimal place. Any values that require transformation to standard units (metric or International System [SI]) will be converted with the appropriate corresponding precision. Details will be provided in the SAP.

Categorical variables will be summarized using counts and percentages. Percentages will be presented to 1 decimal place.

Baseline value, unless otherwise specified, will be defined as the most recent non-missing measurement (scheduled or unscheduled) collected before administration of study drug.

Change (absolute change) from baseline will be calculated as postbaseline value - baseline value.

The treatment-emergent (TE) period will include the time from dosing with study drug to the Safety Follow-up Visit or 28 days after treatment for subjects who do not have a Safety Follow-up Visit.

12.3.2 Background Characteristics

Subject disposition, demographic and baseline characteristics, prior and concomitant medications, and other background characteristics will be summarized. Additionally, all subject data will be presented in subject data listings. All summaries will be based on the FAS, unless otherwise specified in the SAP for the study. No statistical hypothesis testing will be performed on background characteristics.

12.3.2.1 Subject Disposition

Number and percentage of subjects in the following categories will be summarized as appropriate:

- Randomized or dosed (All Subjects Set)
- Randomized
- Dosed (Safety Set)
- Randomized and dosed (FAS)
- Completed 6-Month Follow-up Visit
- Completed study
- Prematurely discontinued the study and the reasons for discontinuation

Subject disposition summary will be presented based on the All Subjects Set.

12.3.2.2 Demographics and Baseline Characteristics

Demographic, background (e.g., medical history), and baseline characteristics will be summarized. Protocol deviations/violations will be provided in a subject data listing only.

The following demographics and baseline characteristics will be summarized by treatment group for the FAS: sex, race, ethnicity, age, weight, height, BMI, country, AIS (A or B with or B without sacral pinprick preservation), and baseline UEMS score.

12.3.2.3 Prior and Concomitant Medications

Medications used in this study will be coded by the World Health Organization Drug Dictionary Enhanced (WHO-DDE) and will be categorized as follows:

- Prior medication: any medication that started prior to dosing with study drug, regardless of when it ended.
- Concomitant medication: medication continued or newly received at or after dosing of study drug through the end of the TE period.
- Post-treatment medication: medication continued or newly received after the TE period.

A given medication can be classified as a prior medication, a concomitant medication, or a post-treatment medication; both prior and concomitant; both concomitant and post-treatment; or prior, concomitant, and post-treatment. If a medication has a missing or partial missing start/end date or time and cannot be determined whether it was received prior to dosing with study drug, concomitantly, or beyond the TE period, it will be considered as prior, concomitant, and post-treatment.

Prior medications and concomitant medications will be summarized descriptively based on the FAS. Post-treatment medications will be listed for each subject.

12.3.2.4 Study Drug Exposure and Compliance

Study drug exposure will be presented in an individual data listing to indicate whether the study drug was administered.

12.3.3 Efficacy Analysis

Assessment of efficacy of VX-210 treatment is 1 of the primary objectives of this pivotal study. A hierarchical testing strategy will be used to preserve the overall 2-sided type I error rate at the 0.05 level. All efficacy endpoints will be analyzed based on the FAS.

